Atrial fibrillation (AF) is a major cause of cardiovascular morbidity and mortality, affecting more than 46 million people worldwide.¹ Direct current cardioversion (DCCV) is used to terminate an episode of symptomatic or hemodynamically unstable AF. The success rate for DCCV is 90-95% and is dependent on patient and procedural characteristics including obesity, use of antiarrhythmic drugs, pad placement, type of shock waveform and shock energy. Biphasic defibrillation waveform shocks improve DCCV success rates for AF to normal sinus rhythm (NSR) compared to monophasic shocks. Various biphasic shock waveforms are available: The Rectilinear Biphasic Waveform (RBW) is used by the Zoll series R defibrillator while the Biphasic Truncated Waveform (BTW) is used in the FDA approved Lifepak model 15 and 20 defibrillators. Despite their routine use in clinical practice, no adequately powered prospective head-to-head randomized controlled trials (RCT) have compared the safety or efficacy of the two biphasic waveforms for DCCV of AF to NSR.

The primary objectives for this pragmatic prospective randomized controlled trial are to 1) compare the efficacy of first shock DCCV from AF to NSR using anterolateral pad placement and a full-output 200J RBW synchronized shock from a Zoll series R defibrillator or a full output 360J BTW synchronized shock from a Lifepak 15 or 20 defibrillator; 2) compare the DCCV efficacy of first or second full output shock 3) compare the DCCV efficacy of third or fourth full output shock after treatment group cross over after first failing 2 consecutive full output shocks from the originally assigned treatment group. The secondary objective is to compare the frequency of skin irritation or damage after first or second shock cardioversion from either defibrillator.

Data will be derived from approximately 560 patients arriving to Inova sites of care in AF scheduled to undergo either AF ablation with expected DCCV or elective stand-alone AF DCCV. Patients will be included if they are in AF prior to their procedure and are willing to sign the consent form and comply with the research procedures. Participants will be excluded if they are in a rhythm other than AF on arrival to IHVI, have not been appropriately anticoagulated with warfarin or direct oral anticoagulant, or have known left atrial appendage thrombus prior to their procedure.

ABBREVIATIONS AND DEFINITIONS

Abbreviation	Definition of Terms
DCCV	Direct Current Cardioversion
RBW	Rectilinear Biphasic Waveform
BTW	Biphasic Truncated Waveform
J	Joules
AF	Atrial Fibrillation
IHVI	Inova Heart and Vascular Institute
NSR	Normal Sinus Rhythm

PROTOCOL SYNOPSIS

Study Title:	A Pragmatic Randomized Clinical Trial Comparing Rectilinear Biphasic Waveform and Biphasic Truncated Exponential Waveform Shocks for Cardioversion of Atrial Fibrillation (Zoll vs Lifepak-RCT)
Source of Funding:	N/A
Clinical Phase:	N/A
Study Rationale:	
Atrial fibrillation (AF) is a major cause of cardiovascular morbidity and mortality, affecting more than 46 million people worldwide.¹ Direct current cardioversion (DCCV) is used to terminate an episode of symptomatic or hemodynamically unstable AF. The success rate for DCCV is 90-95% and is dependent on patient and procedural characteristics including obesity, use of antiarrhythmic drugs, pad placement, type of shock waveform and shock energy. Biphasic defibrillation waveform shocks improve DCCV success rates for AF to normal sinus rhythm (NSR) compared to monophasic shocks. Various biphasic shock waveforms are available: The Rectilinear Biphasic Waveform (RBW) is used by the Zoll series R defibrillator while the Biphasic Truncated Exponential Waveform (BTE) is used in the FDA approved Lifepak 15 or 20 defibrillator. Despite their routine use in clinical practice, no adequately powered prospective head-to-head randomized controlled trials (RCT) have compared the safety or efficacy of the two biphasic waveforms for DCCV of AF to NSR.
 
The primary objectives for this pragmatic prospective randomized controlled trial are to 1) compare the efficacy of first shock DCCV from AF to NSR using an anterolateral pad placement and full-output 200J RBW synchronized shock from a Zoll series R defibrillator and a full output 360J BTW synchronized shock from a Lifepak 15 or 20 defibrillator; 2) compare the DCCV efficacy of first or second full output shock 3) compare the DCCV efficacy of first or second crossover full output shock after first failing 2 consecutive full output shocks from the other

A Pragmatic Randomized Clinical Trial Comparing Rectilinear Biphasic Waveform and Biphasic Truncated Exponential Waveform Shocks for Cardioversion of Atrial Fibrillation (Zoll vs Lifepak-RCT) |

PI: [name]

	defibrillator. The secondary objective is to compare the frequency of skin irritation or damage after first or second shock cardioversion from either defibrillator.
Study Objective(s):	
Primary:
 
 1. To compare the efficacy of a single 200J RBW shock and a single 360J BTE shock 2. To compare the efficacy of one or two consecutive 200J RBW or 360J BTE shocks 3. To measure the efficacy of cross over from RBW to BTE or BTE to RBW after failing 2 consecutive full output shocks with the first waveform 
Secondary:
 
 1. To compare the frequency of adverse events after one or two 200J RBW or 360J BTE shocks
Test Product(s)/Agent(s):	
 1. Zoll Series R Defibrillator (RBW shock waveform, maximum output 200J) 2. Physiocontrol Lifepak 15 or 20 Defibrillator (BTE shock waveform, maximum output 360J)
Study Design:	Single center, investigator-initiated, open label prospective randomized controlled trial
Participant Population Key Criteria for Inclusion and Exclusion:	
Inclusion Criteria:
 
 ▪ Adults aged ≥ 18 years of age in AF scheduled to undergo DCCV or catheter ablation with expected DCCV 
Exclusion Criteria:
 
 ▪ Patients with arrhythmias other than AF, hemodynamically unstable AF, untreated hyperthyroidism, known or suspected pregnancy, those in another trial. Patients will be required to have received sufficient anticoagulation or computed tomography angiography scan or transesophageal echocardiogram documenting the absence of intracardiac thrombi.
Number of Participants:	A total of 560 unique study subjects will be enrolled.

A Pragmatic Randomized Clinical Trial Comparing Rectilinear Biphasic Waveform and Biphasic Truncated Exponential Waveform Shocks for Cardioversion of Atrial Fibrillation (Zoll vs Lifepak-RCT) |

PI: [name]

Study Duration:	Each subject's participation will last from screening until 1 minute after the final DCCV shock is delivered.
Study Phases:	
 1. Screening: Patients arriving in AF scheduled to undergo DCCV or AF ablation with possible DCCV at an Inova site of care will be screened in the peri-procedure holding area. 2. Intervention: Patients will be randomized to a Zoll or Lifepak defibrillator to perform the DCCV. All shocks will be full output (200J for Zoll shocks and 360J for Lifepak shocks). Follow up will be assessment and documentation of rhythm 1 minute after the last shock is delivered.
Efficacy Evaluations:	
 1. Proportion of patients in NSR by ECG or monitor 1 minute after the first DCCV shock. 2. Proportion of patients in NSR by ECG or monitor 1 minute after the first or second DCCV shock. 3. Proportion of patients in NSR by ECG or monitor 1 minute after a third or fourth crossover treatment assignment shock after failing first and second shock on original treatment assignment.
Safety Evaluations:	
 1. Number of patients with skin redness, pain or discomfort under the shock electrodes (excluding those with cross-over) 2. Number of patients with arrhythmic events (asystole, atrioventricular block, transient bradycardia or ventricular arrhythmia) within 10 minutes of the last DCCV shock 3. Frequency of pacemaker or ICD dysfunction after shock among patients with prior pacemaker or defibrillator implant
Statistical and Analytical Plan:	
Based on the best available literature we expect the first shock DCCV success rate to be 93% in our population. A total sample size of 538 subjects (269 in each group) will be needed to provide 80% power to reject the null hypothesis (a difference of efficacy < 5%). The analysis will be performed on the intention-to-treat population. The proportions will be compared using both risk difference and risk ratio with corresponding 95% CI. Effects of treatment will be estimated by modified

A Pragmatic Randomized Clinical Trial Comparing Rectilinear Biphasic Waveform and Biphasic Truncated Exponential Waveform Shocks for Cardioversion of Atrial Fibrillation (Zoll vs Lifepak-RCT) |

PI: [name]

	Poisson regression using generalized estimating equations. Outcomes will be compared across pre-specified subgroups and testing will be performed for interactions (sex, body mass index, first or > 1 AF episode, AF type, DCCV location).
Data and Safety Monitoring Plan:	The study PI will be responsible for study safety. One interval analysis will be performed after 50% trial enrollment. No DSMB will be assembled.

TABLE OF CONTENTS

STUDY TITLE.....	Error! Bookmark not defined.
SUMMARY OF CHANGES	i
ABSTRACT	ii
ABBREVIATIONS AND DEFINITIONS.....	iii
PROTOCOL SYNOPSIS	iv
TABLE OF CONTENTS	viii
SCHEMA EXAMPLES.....	Error! Bookmark not defined.
1. BACKGROUND.....	2
1.1 Study Disease(s) or Condition(s)	2
1.2 Product(s) / Agent(s)	2
1.3 Rationale	3
1.4 Relevant Literature and Data	3
1.5 Correlative Studies Background	5
1.6 Compliance Statement.....	5

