17.2	Participant Discontinuation/Withdrawal from the Study	17
17.3	Early Termination Study Visit	Error! Bookmark not defined.
18.	RECORDINGS.....	18
19.	IRB REVIEW HISTORY	18
20.	COORDINATING CENTER for MULTI-Site Studies	18
20.1	Participating Sites	18
20.2	Description of Collecting Sites.....	18
20.3	Study-Wide Number of Participants.....	18
20.4	Communication to Participating Sites	18
21.	REFERENCES / BIBLIOGRAPHY	18

A Pragmatic Randomized Clinical Trial Comparing Rectilinear Biphasic Waveform and Biphasic Truncated Exponential Waveform Shocks for Cardioversion of Atrial Fibrillation (Zoll vs Lifepak-RCT) |

PI: [name]

A Pragmatic Randomized Clinical Trial Comparing Rectilinear Biphasic Waveform and Biphasic Truncated Exponential Waveform Shocks for Cardioversion of Atrial Fibrillation (Zoll vs Lifepak-RCT) |

PI: [name]

Study Phase	Screening (Pre-Op)	Treatment/Intervention (EP Lab or CDU Procedure Suite)
Informed Consent/Assent	X	
Review Inclusion/Exclusion Criteria	X	
Duration of AF Assessment (< 7 days, 7 days-365 days, > 365 days)	X	
Months since AF diagnosis	X	
Prior DCCV?	X	
CHA2DS2VASC score	X	
Moderate or Severe Valvular Disease?	X	
Heart Failure with Reduced Ejection Fraction?	X	
Body Mass Index	X	
Date of Birth	X	
Sex	X	
Pregnancy Test	X	
Amiodarone (yes/no)	X	
Flecainide (yes/no)	X	
Beta blockers (yes/no)	X	
ACE Inhibitor or ARB (yes/no)	X	
Randomization	X	
DCCV		X
ECG or Monitor 1 minute after 1 st shock		X
Adverse Event Assessment 10 minutes after shock or at conclusion of procedure		X

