9.2 Study Intervention Visit

9.2.1 At the study visit the patient will be connected to the randomly allocated defibrillator, connector cable, and pads. Pads will be placed in an anterolateral location unless this is impossible, in which case pads will be applied in alternative locations. After sedation is provided the patient will undergo DCCV at full output (200J for the Zoll Series R device and 360J for the Lifepak Series 15/20 device). After the procedure is complete the pads will be removed and the site assessed for erythema or burns 10 minutes or more after the last administered shock.

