12. DATA ANALYTICS

12.1 Study Endpoints

Efficacy assessments for the primary endpoints will occur using data obtained at screening and the DCCV study visit. Specifically, the endpoint of NSR will be acquired by monitoring strip or 12 lead ECG 1 minute after each DCCV shock is delivered.

Primary Endpoints

- 12.1.1 The frequency of NSR one minute after a single full output DCCV shock is delivered by a Zoll Series R RBW waveform defibrillator and a Lifepak Series 15/20 BTE waveform defibrillator.
- 12.1.2 The frequency of NSR one minute after the first or second full output DCCV shock is delivered by a Zoll Series R RBW waveform defibrillator and a Lifepak Series 15/20 BTE waveform defibrillator.
- 12.1.3 The frequency of NSR one minute after the first or second full output DCCV shock is delivered by a Zoll Series R RBW waveform defibrillator and a Lifepak Series 15/20 BTE waveform defibrillator after crossing over from the alternative defibrillator after failing 2 consecutive full output shocks at maximum output.

Secondary Endpoints

- 12.1.4 The frequency of adverse events including skin irritation, pain, or burning; arrhythmic events including asystole, atrioventricular block, transient bradycardia or ventricular arrhythmia within 10 minutes of the last DCCV shock; and the frequency of pacemaker or ICD dysfunction after shock among patients with prior pacemaker or defibrillator implant. Transient bradycardia will be defined as symptomatic bradycardia requiring the use of temporary pacing, atropine, isuprel, or epinephrine for rate support. The secondary safety endpoint will be assessed only among patients who do not cross-over from one defibrillator to the other.

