12.1.5 End of Study Definition

A participant is considered to have completed the study if he or she has completed all phases of the study including screening, enrollment,

PI: [name]

procedure and the 10 minute skin assessment after pad removal.

The end of the study is defined as completion of the last visit shown in the Schedule of Activities.

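### The synopsis closes participation 1 minute after the last shock, and the schedule allows adverse event assessment at the end of the procedure, but the arrhythmic safety endpoint runs to 10 minutes

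*Combined protocol and SAP*

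**What the plan says.** **End of participation.** The Protocol Synopsis, under Study Duration, says: "Each subject's participation will last from screening until 1 minute after the final DCCV shock is delivered". Under Study Phases it describes follow-up as a rhythm check only: "Follow up will be assessment and documentation of rhythm 1 minute after the last shock is delivered".

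**Safety endpoint.** Section 12.1.4 lists, among other adverse events, "arrhythmic events including asystole, atrioventricular block, transient bradycardia or ventricular arrhythmia within 10 minutes of the last DCCV shock". The Safety Evaluations row of the synopsis gives the same 10 minutes from the last shock. Section 6.1 also places a 10-minute follow-up within the procedure day.

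**Timing of the assessment.** The schedule of activities has "Adverse Event Assessment 10 minutes after shock or at conclusion of procedure". Section 9.2.1 has pads removed once the procedure is complete and the "site assessed for erythema or burns 10 minutes or more after the last administered shock". Section 12.1.5 makes completion of the study depend on the "procedure and the 10 minute skin assessment after pad removal".

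**Closing the record.** Section 11.1 has the case report form completed when the procedure concludes, with no need for study staff to be present. Section 5.3 has clinical staff attach the 1-minute strip and seal the envelope.

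**The concern.** Adverse events are the plan's only secondary endpoint, and comparing their frequency between the two devices is its only secondary objective. The comparison needs each patient to be watched, and the form kept open, for the whole period over which events count.

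Two pieces of text allow less. The synopsis ends participation and follow-up well inside the 10-minute window. The schedule offers the end of the procedure as an alternative assessment time, with no condition that 10 minutes have passed. Staff who follow either text would comply with the protocol and could still miss an event that the endpoint is meant to count. The frequency of asystole, atrioventricular block, treated bradycardia or ventricular arrhythmia could then be understated.

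**Working it through.** The plan gives no figure to reproduce. The check sets the timing statements side by side, with time measured from the last shock unless noted.

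| Place | What is timed | Time |
|---|---|---|
| Synopsis, Study Duration | End of participation | 1 min |
| Synopsis, Study Phases | Follow-up (rhythm only) | 1 min |
| Synopsis, Safety Evaluations | Arrhythmic events | to 10 min |
| Section 12.1.4 | Arrhythmic events | to 10 min |
| Section 6.1 | Follow-up | 10 min |
| Schedule of activities | Adverse event assessment | 10 min after shock (which shock is not said), or end of procedure |
| Section 9.2.1 | Skin check | 10 min or later |
| Section 12.1.5 | Skin check | a 10-minute check, after pad removal |
| Section 11.1 | Case report form completed | end of procedure |

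**Step 1: synopsis against endpoint.** Window 10 min, participation 1 min: 10 − 1 = 9 minutes of the window fall after the stated end of participation. This describes the wording. It does not estimate lost events.

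**Step 2: schedule against endpoint.** Let T be the minutes from last shock to the end of the procedure. If assessment and form are closed at T, the uncovered part of the window is max(0, 10 − T). The documents do not give T, so a range has to be assumed. At T = 1 (just after the rhythm check) 9 minutes are uncovered, at T = 5 it is 5 minutes, and at T of 10 or more it is none. Short stand-alone cardioversions are the exposed group. An ablation that continues for 10 minutes or more after the shock is not exposed.

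**Step 3: does another section close the gap?** Only in part. Section 12.1.5 requires the skin check before a participant counts as complete, and section 9.2.1 puts that check at 10 minutes or later. Both concern skin and do not say that rhythm events are sought or recorded up to that time. Section 9.2.1 also places the skin check after the procedure is complete, whereas section 11.1 has the form completed when the procedure concludes. No section reconciles these.

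**Step 4: events after the first shock.** Section 2.2.1 covers adverse events after one or two shocks, but the arrhythmic window refers only to the last. Section 5.1.3 sets a minimum of 1 minute between shocks and no maximum. Taking the window to reach 10 minutes to either side of the last shock, an event soon after shock 1 falls outside it only if shock 2 comes more than 10 minutes later. Section 12.2 assumes 93% first-shock success, so about 7% need a second shock: 0.07 × 560 = 39.2, roughly 39 patients. How many of them would have so long a gap is not stated. Crossover patients are excluded from this endpoint, so later gaps do not matter.

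**The case against.** The strongest reply is that the plan's intention is clear. The arrhythmic window is the same in both places that define it. Sections 6.1, 9.2.1, 12.1.4 and 12.1.5 all refer to 10 minutes, which leaves the 1-minute line in the synopsis as an outlier. Section 13.2 adds that adverse events are monitored throughout the study. Much of this stands: the plan does not contain several rival arrhythmia windows. It does not remove the conflict, because the synopsis and the schedule are operative text, and section 12.1.5 itself defines the end of the study by reference to the schedule.

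A reader might infer more than the documents support:

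- **A separate window from pad removal.** Section 12.1.5 most naturally names the section 9.2.1 skin check, done once the pads are off. The wording is ambiguous, but it is not a definite extra window, and it never governs arrhythmias.
- **Bias between devices.** Staff are unblinded, but nothing shows that timing would follow the assigned device. Variation is likeliest between ablation and stand-alone procedures, and section 5.3 blocks randomization by location, which should help balance it.
- **Missed events entered as no event.** Section 11.1.3 refers to the case report form for the exact fields. That form is not in the documents, so neither this nor an absence of clock times can be asserted.
- **All 560 patients affected.** Crossover patients are removed from the safety endpoint.
- **First-shock events definitely lost.** This is possible under the wording, but only in the narrow case described above.

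**Conclusion.** The plan is inconsistent as written and should be corrected. The end of participation in the synopsis and the end-of-procedure option in the schedule both allow close-out before the 10-minute arrhythmic window has run. Up to 9 of the 10 minutes can fall outside stated participation. How many events would be missed cannot be estimated, because the documents give neither event rates nor the time from shock to end of procedure.

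The effect is confined to the secondary safety endpoint in non-crossover patients, and in practice to procedures that end within 10 minutes of the last shock. Sinus rhythm at 1 minute is unaffected. The conclusion assumes that staff may act on the synopsis and schedule as written. It does not depend on any difference between devices.

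**What to change.** 1. In the synopsis (Study Duration and Study Phases), end participation only after the 10-minute arrhythmic window and the skin check, in line with the synopsis safety row and sections 6.1, 9.2.1 and 12.1.4.
2. In the schedule of activities, delete the end-of-procedure alternative, since it can fall before 10 minutes, and say that the time runs from the last shock.
3. In section 11.1, have the case report form closed only after both assessments. Bring the envelope-sealing step in section 5.3 into line.
4. In section 12.1.5, state that the skin assessment is the one in section 9.2.1, timed from the last shock.
5. In section 12.1.4 and the synopsis safety row, count arrhythmic events from the first study shock through 10 minutes after the last, so that the endpoint matches the objective in section 2.2.1.

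An upper time limit on the skin reading would be a reasonable preference, but the correction does not depend on it. The cost is wording in a handful of places and a few minutes' longer observation for some stand-alone patients. Sample size, randomization and the primary analysis are unchanged.

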11.1.3 Data Fields

Please see the case report form for exact data collected. Identifiers collected will include name, Inova medical record number, date of birth, and date of DCCV procedure.

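### The primary regression names no covariates, although the plan itself identifies obesity and antiarrhythmic drug use as determinants of success and collects data on both

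*Combined protocol and SAP*

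**What the plan says.** The Abstract and the Synopsis rationale describe success as "dependent on patient and procedural characteristics including obesity, use of antiarrhythmic drugs, pad placement, type of shock waveform and shock energy". Two of these are patient characteristics measurable at baseline: obesity and antiarrhythmic drug use.

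The schedule of procedures, placed before section 1, lists at screening BMI, "Amiodarone (yes/no"), "Flecainide (yes/no"), beta blockers and ACE inhibitor or ARB. It has no item for any other antiarrhythmic drug. Section 11.1.3 leaves the definitive field list elsewhere: "Please see the case report form for exact data collected". That form is not among the documents.

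The Synopsis says that treatment effects will be estimated by modified "Poisson regression using generalized estimating equations" and names no covariate. It then says: "Outcomes will be compared across pre-specified subgroups and testing will be performed for interactions (sex, body mass index, first or > 1 AF episode, AF". The list ends with AF type and cardioversion location. Section 12.2 gives the sample size and the intention-to-treat principle but adds nothing on adjustment. Section 5.3 blocks the 1:1 randomization by treatment location (electrophysiology lab or elsewhere) and by nothing else.

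**The concern.** A plan that calls a baseline characteristic prognostic and collects it would normally say how the analysis uses it. Here BMI enters only as a subgroup factor, drug use enters nowhere, and the randomization factor is not in the model.

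Two modest things are at stake. First, precision: a chance imbalance in a prognostic factor stays in the unadjusted estimate. Second, pre-specification: patients, staff and investigators all know the allocation, and the Synopsis plans an analysis at 50% enrollment with no independent board. Covariates chosen later could be chosen by people who have seen outcomes by arm.

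**Working it through.** **Inputs from the documents.** First-shock success 93%, difference of interest 5 points, 272 per arm and 80% power (section 12.2); 269 per arm (Synopsis). The significance level is not stated; two-sided 0.05 is assumed, in line with the planned 95% intervals.

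**Inputs assumed.** The documents give neither the share of patients on an antiarrhythmic drug (q) nor the difference in success by drug use (d). The ranges used are q = 20 to 50% and d = 3 to 10 points.

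**Step 1: reproduce the plan's figure.** For 93% v 98% with pooled variance and no continuity correction, the mean proportion is 0.955:

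n = [1.96·√(2·0.955·0.045) + 0.8416·√(0.93·0.07 + 0.98·0.02)]² / 0.05² = (0.5746 + 0.2449)² / 0.0025 ≈ 268.7, so 269 per arm.

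This matches the Synopsis total of 538. At 272 per arm, power is 80.5%.

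**Step 2: gain from adjustment for drug use.** The share of outcome variance explained is R² = q(1−q)d² / [0.93·0.07], the required total becomes 544·(1−R²), and the standard error shrinks by 1−√(1−R²).

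| q | d | R² | equivalent total N |
|---|---|---|---|
| 20% | 3 points | 0.2% | 543 |
| 30% | 5 points | 0.8% | 540 |
| 30% | 8 points | 2.1% | 533 |
| 50% | 10 points | 3.8% | 523 |

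- R² of 1%: standard error down 0.5%, power 80.5% to 80.9%.
- R² of 2%: standard error down 1.0%, power 81.3%.
- R² of 3.5%, near the extreme corner: standard error down 1.8%, power 81.9%.

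**Step 3: check on the planned scale.** The endpoint is sinus rhythm, so the regression gives a risk ratio for success. Its log has standard error √[0.07/(272·0.93) + 0.02/(272·0.98)] ≈ 0.019. A risk ratio for failure would have √[0.93/(272·0.07) + 0.98/(272·0.02)] ≈ 0.48, so a gain worked out on the failure scale is not the planned analysis. Simulated trials of 272 per arm at 93% v 98% were each analysed with and without BMI and drug use. Odds ratios for failure of 2 to 3 off drug and 1.08 to 1.12 per BMI unit were assumed. Standard errors on the success scale fell by about 0.5 to 1%. Power rose by 0.1 to 0.5 points, which is within simulation noise.

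**Step 4: size of chance imbalance.** The between-arm difference in drug prevalence has SD √[2q(1−q)/272], which is 3.4 points at q = 20% and 4.3 at q = 50%. An imbalance of 1.96 SD shifts the unadjusted risk difference by 1.96·0.034·3 ≈ 0.2 points up to 1.96·0.043·10 ≈ 0.8 points, against a 5-point target.

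**Step 5: how many covariates the data can carry.** Expected first-shock failures at 93% v 98% are 272·0.07 + 272·0.02 = 19.0 + 5.4 ≈ 24. Device, BMI, drug use and location make four coefficients, or about 6 failures each.

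**Step 6: could drug use be a tested subgroup?** Suppose 93% v 98% off drug and 93% in both arms on drug. The standard error of the interaction is √[0.0847/(272(1−q)) + 0.1302/(272q)], where 0.0847 = 0.93·0.07 + 0.98·0.02 and 0.1302 = 2·0.93·0.07. This is 0.0528 at q = 20% and 0.0398 at q = 50%. Power to detect the 5-point interaction is about 16% and 24%.

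**The case against.** The strongest reply is that nothing here threatens validity. Allocation is randomized and the analysis is by intention to treat, so omitting a baseline prognostic factor does not bias the comparison, and the confidence interval already allows for chance imbalance. The gain is close to nil and rests on assumed effects. BMI already has a pre-specified role as a subgroup factor. All of this stands, and it limits the point to efficiency and pre-specification.

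A reader might go further and infer that drug exposure is misclassified, with users of other rhythm drugs contaminating an unexposed group. The documents do not support that. The two drug items are correct for what they ask, and the plan defines no any-antiarrhythmic variable that could be wrong. Nor can it be said that only two drugs are captured, because section 11.1.3 defers to a form that was not supplied. The schedule is not the full field list either: section 9.1.3 requires heart rate and blood pressure, which it omits. The narrower statement holds: if the two items were combined into any v none, users of unlisted drugs would count as none. For scale only, if 40% took an antiarrhythmic and 25 to 50% of those took an unlisted one (assumptions), 0.10/0.70 = 14% to 0.20/0.80 = 25% of apparent non-users would be users.

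A reader might also think the ACE inhibitor or ARB item is a wasted field. Baseline items may simply describe the population, and no space limit is documented.

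**Conclusion.** The point holds as a minor improvement. The plan names two patient-level determinants of success and schedules BMI and two antiarrhythmic drugs for collection, yet it specifies no covariates and gives drug use no analysis role. The benefit of adjustment is about 0.5 to 1% in the standard error and at most about 1 power point under plausible assumptions (1.4 points near the most favourable corner of the range), plus protection against chance imbalance and post hoc choice of covariates. These sizes depend on assumed drug prevalence and effects, which the documents do not give.

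It would be wrong to conclude that the planned analysis is biased or that the sample size must change. Neither follows. A drug subgroup could not settle whether the device difference depends on drug use, however well the drugs are recorded.

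**What to change.** In the Synopsis and section 12.2, state that the primary modified Poisson model for first-shock success will include continuous BMI, baseline antiarrhythmic use (any v none) and treatment location. Location belongs there because randomization is blocked by it. Report the unadjusted risk difference and risk ratio alongside, and say which analysis is primary.

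Check the case report form. If it has no such item, add one for any other current antiarrhythmic drug, by name, so that any v none is complete. No existing field needs to go. If results by drug use are shown, label them descriptive.

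The cost is one sentence in two places and possibly one form field, filled from the chart review already described in section 8.1.2. The downside is the small number of failures: the list should stay at these three covariates, and since failures after two shocks cannot exceed those after one, it should not be lengthened for the later endpoints.
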